12.2.6.2 Radiation Dosimetry Analysis of ¹⁷⁷Lu-3BP-227

The radiation dosimetry analysis of the radiopharmaceutical ¹⁷⁷Lu-3BP-227 will be performed by an independent expert under the responsibility of the sponsor's Clinical Pharmacokinetics and Pharmacometrics department.

Further details on dosimetric assessments and on dosimetric parameters will be provided in a Dosimetry Assessment Plan.

The dosimetric assessments will be performed and reported according to the criteria set out by the European Association of Nuclear Medicine Dosimetry Committee guidance document: good practice of clinical dosimetry reporting [32].

Calculations will be conducted for the following parameters (only in organs showing uptake):

- organs receiving the highest absorbed dose
- specific absorbed dose to the target lesion (Gy/GBq)
- specific absorbed dose per organ (Gy/GBq)
- cumulative absorbed organ doses (Gy).

Cumulative absorbed organ doses (Gy) and organs of highest radioactivity uptake will be identified visually. Regions of interest will be placed over these organs to determine the relative activity in the respective organs. Time activity curves (describing % IA/ROI of the activity amount injected versus time, considering renal excretion activity) will be derived. The absorbed doses of the dose-limiting organs (kidney, bone marrow and liver) will be evaluated and reported to the investigator before the next administration of ¹⁷⁷Lu-3BP-227 can be initiated to enable activity adaptations in the event the next dose may exceed the organ limits of 23 Gy (kidney), 2 Gy (bone marrow) and 30 Gy (liver). The dosimetry results for all other organs will be finalized for the final study report with the restriction that the dosimetry data must be available for the SRC meeting. These data can be reviewed at any time if a major safety issue occurs.

The proportion of renally excreted radioactivity, whole blood radioactivity, and dosimetric whole body images will be used to calculate the dosimetry of ¹⁷⁷Lu-3BP-227.

12.2.6.3 Pharmacokinetic Analysis of 3BP-227

The PK analysis of 3BP-227 will be performed under the responsibility of the sponsor's Clinical Pharmacokinetics and Pharmacometrics department.

Analysis of PK data by a noncompartmental approach will be documented in a separate SAP. Individual plasma and urine concentrations of 3BP-227 will be listed and summarised by time points using descriptive statistics for continuous variables (number of available observations, mean, median, standard deviation, minimum, maximum, geometric mean, and geometric coefficient of variation assuming lognormally distributed data). Linear and semilogarithmic plots of individual and mean plasma concentration-time profiles as well as spaghetti plots will be reported.

Any suspicious concentration will be investigated and kept in the PK analysis if possible. All excluded concentrations will be justified in the report.

If 3BP-227 levels are measurable in plasma and urine, PK parameters of 3BP-227 (including, but not limited to, C_{max} , AUC, $t_{1/2}$, Cl, Vd, Ae, CL_R) will be derived using the noncompartmental approach on the individual plasma concentration-time profiles of 3BP-227 and on the individual urine concentrations.

An attempt to build an integrated model taking into account PK, dosimetry as well as efficacy and safety data will be made if warranted by the data. The exploratory analysis will be captured in a separate data analysis plan and reported in a standalone report.

12.2.7 Pharmacodynamic/Efficacy Evaluation

For phase I, tumour response will be evaluated only by the site investigator, using the revised RECIST guideline version 1.1 (see Attachment 4, Section 19.4). Only subjects with measurable disease at baseline, who have received at least two administrations of ¹⁷⁷Lu-3BP-227 and reached the end of Cycle 2 or EOCT visit would be considered evaluable for response.

All measurable lesions up to a maximum of two lesions per organ and five lesions in total, representative of all involved organs, should be identified as target lesions and recorded and measured at baseline. Target lesions should be selected on the basis of their size (lesions with the longest diameter), be representative of all involved organs and permit reproducible repeated measurements. On occasion, if the largest lesion does not permit reproducible measurement,

the next largest lesion which can be measured reproducibly will be selected. A sum of the diameters (longest for non-nodal lesions, short axis for nodal lesions) for all target lesions will be calculated and reported as the baseline sum diameters. If lymph nodes are included in the sum, then only the short axis will be added into the sum. The baseline sum of diameters will be used as reference to further characterise any objective tumour regression in the measurable dimension of the disease.

All other lesions (or sites of disease) including any measurable lesions over and above the five target lesions should be identified as nontarget lesions and should also be recorded at baseline. Measurements of these lesions are not required, but the presence, absence, or unequivocal progression of each should be noted throughout follow-up.

Subjects will be evaluated as CR, PR, SD, PD, or inevaluable according to RECIST version 1.1. Based on this classification, the following endpoint will be calculated as defined by RECIST version 1.1 and below.

- Objective Response Rates (ORR): proportion of subjects with a best overall response (BOR) characterised as either a Complete Response (CR) or Partial Response (PR) relative to the total number of evaluable subjects
- Disease control rate (DCR): proportion of subjects with a BOR characterised as CR, PR or SD relative to the total number of evaluable subjects

The PFS and OS will also be evaluated as defined per RECIST version 1.1.

Details of the response evaluation will be given in a separate image review charter. Details of the analysis will be specified in the SAP.

Efficacy data will be summarised using descriptive statistics and will be graphically displayed, if appropriate. The correlation between pharmacodynamic parameters and selected safety, efficacy, or PK parameters may be graphically displayed. Further statistical analyses may be conducted. Details of the response evaluation will be given in a separate image review charter. Details of the analysis will be specified in the SAP.

An attempt to build an integrated model taking into account PK, dosimetry as well as efficacy and safety data will be made, if warranted by the data. The exploratory analysis will be captured in a separate data analysis plan and reported in a standalone report.

12.2.8 Interim Analysis/Safety Review Committee

During the dose escalation part and before each decision on further dose escalation, safety and dose limit organ exposure data will be summarised and presented to the SRC. This SRC will be set-up for the dose escalation decisions (after the end of the third subject's Cycle 1) and second dosing cycle (after the end of the third subject's Cycle 2).

At the time of SRC meeting, all cumulative available information will be reviewed.

A continual reassessment method (CRM) in conjunction with a Bayesian approach modelling of DLT rates and radiation exposure to target organs may be performed during the planned review meetings to generate additional relevant information for the adaptive dose selection decisions. PK and pharmacodynamic data may be also incorporated in the model. The SRC will review all available data and make the final decision as to dose escalation, de-escalation, or cohort expansion during the adaptive dose-escalation phase. This group will also determine when to implement predefined stopping rules.

An interim analysis of the escalation cohort data may be done when the MTCA or MACA have been determined.

A specific charter will be developed to define roles and responsibilities, as well as the data set to be reviewed by the SRC.

Full analysis will be performed on the entire dataset at the EOCT and at the end of the long-term follow-up.

12.2.9 Clinical Study Report

A final clinical study report (CSR) will be prepared according to the International Council for Harmonisation (ICH) guideline on structure and contents of CSRs. A final CSR will be prepared where any subject has signed informed consent, regardless of whether the study is completed or prematurely terminated. Where appropriate an abbreviated report may be prepared. The CSR will comply with any applicable regulatory requirements, national laws in force and will be in English.

As indicated in Section 12.2.8, a full analysis based on all data recorded until the last subject completed their EOCT visit will be performed. This analysis will be included in a CSR. An addendum to the report will be prepared, including all data recorded from the follow-up period and additional cycles that occurred after the first data cut-off.

12.3 Statistical Methodology for Phase II

12.3.1 Sample Size Calculation

In case the antitumour activity is driven by a type of tumour, tumour-specific phase II cohort(s) will be initiated utilising an Optimal Simon Two-Stage design [33] to further evaluate the antitumour activity of ¹⁷⁷Lu-3BP-227. This approach tends to minimise the average number of subjects exposed to a new drug while addressing the scientific question.

The corresponding hypotheses (H) to be tested are: H_0 : ORR \leq ORR₀ versus H_1 : ORR \geq ORR₀ where ORR is the true objective response rate following 177 Lu-3BP-227 treatment and ORR₀ is the minimum objective response rate that would be considered to further clinical development.

For the purpose of the a priori sample size calculation, the following values are used for the PDAC cohort: ORR_0 is 17% and ORR is 35%. These values reflect the results from PDAC therapy [34] currently registered and are considered standard-of-care, and the level of expectation for the IMP prior to phase I.

Similarly, for the CRC cohort (blended population with regard to somatic mutations in BRAF and RAS genes), ORR₀ is 15% and ORR is 30% [35;36]. The value for ORR₀ reflects an estimated average result from different clinical studies that investigated CRC therapies in different populations [35, 36]; it is anticipated that based on lack of available and effective therapies an enrichment of poor-prognosis subjects with metastatic and recurrent CRC and prevalent mutations in BRAF and RAS will occur in the study population, while it is anticipated that it is unlikely for subjects with wild-type disease for which effective therapies exist over multiple lines of treatment to be enrolled. Subjects with somatic BRAF and RAS mutations are anticipated to have less exposure to prior treatment for metastatic disease compared with subjects with prevalent wild type BRAF or RAS tumours.

The assumptions forming the understanding of the expected efficacy of standard-of-care treatment and leading to sample size estimations may be updated based on results emerging from phase I and evolving scientific knowledge.

In the first stage of the design, for the PDAC cohort, 16 subjects will be treated and evaluated for the ORR. If there are three or fewer responders in these 16 subjects, the cohort will be stopped for futility. Otherwise, 28 additional subjects will be treated and evaluated for a total of 44 subjects. The null hypothesis will be rejected if 12 or more responders are observed in the 44 subjects. This design yields a nominal one-sided type I error rate of 5% and a power of 80%, if the true response rate is 35%.

Similarly, in the first stage of the design, for the CRC cohort 19 subjects will be treated and evaluated for the ORR. If there are three or fewer responders in these 19 subjects, the cohort

will be stopped for futility. Otherwise, 36 additional subjects will be treated and evaluated for a total of 55 subjects. The null hypothesis will be rejected if 13 or more responders are observed in the 55 subjects. This design yields a nominal one-sided type I error rate of 5% and a power of 80%, if the true response rate is 30%.

Nonevaluable subjects will be replaced to meet the above numbers of evaluable subjects. A subject will be considered as nonevaluable and therefore replaced, if no evaluation post treatment is available or in case of drop-out before the 4-month visit for PDAC cohort and 8-month visit for CRC cohort with an insufficient follow-up duration (i.e. status being still "Stable Disease" as per RECIST version 1.1). In case of overenrollment, the first 16 evaluable subjects in the PDAC cohort and 19 subjects in the CRC cohort will be analysed at Stage 1 to make the decision about starting Stage 2. Assuming a non-evaluability rate of 20% for the PDAC cohort [34] and the CRC cohort [36], the number of subjects to be enrolled is expected to be approximately 55 and 70, respectively.

One, two or three further cohorts may be initiated (subject to results emerging from ongoing preclinical studies and antitumour efficacy seen during dose escalation and amending the current protocol) likely to enrol approximately 120 subjects with GC, SCCHN and/or ES.

In the case of acceptable tolerability and evident antitumour activity across all enrolled subjects in phase I, a phase II basket trial design will be utilised to study the antitumour activity of ¹⁷⁷Lu-3BP-227 in subjects with NTSR1 expressing tumours. The sample size will be described as part of a protocol amendment.

Subjects in each phase of the study will have a 5-year safety follow-up after the EOCT, ED or EOAC visit. The dose, the number and length of cycles in phase II will be refined according to phase I results.

However, if the antitumour activity is driven by a type of tumour, tumour-specific phase II cohort(s) will be initiated utilising an Optimal Simon's Two Stage design (see Phase II).

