12.3.2 Analysis Sets

All subjects who receive at least one dose of the study drug will be included in the safety evaluation. All subjects who receive at least one dose of study drug and who have postbaseline efficacy data for the ORR will be included in the efficacy evaluations of the primary endpoint. All subjects who receive at least one dose of study drug and who have any postbaseline secondary efficacy data will be included in the efficacy evaluations of the secondary endpoints.

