12.3.4 Efficacy Evaluation

Tumour response will be assessed in imaging studies of CT or MRI scans after cycle 2 and subsequently every 8 weeks for the first 6 months and every 12 weeks thereafter.

The primary endpoint is ORR and will be calculated as defined in RECIST version1.1 and in Section 12.2.7. As part of secondary efficacy endpoints, DCR, TTP, Time to response (TTR), DOR, PFS and OS will also be determined as defined by RECIST version 1.1, metabolic response will also be determined as defined by PERCIST version 1.0.

In the particular context of the Simon Two-Stage approach, ORR will be analysed at the end of Stage 1 (and no later than after the 16-week visit of the last evaluable subject of the Stage 1 cohort for each PDAC and CRC cohorts). If the observed number of responders is below a predefined threshold, this part of the study will be stopped for futility. Otherwise, additional subjects will be treated to complete the planned enrolment. At the end of Stage 2, the null

hypothesis will be rejected depending on the total observed number of responders based on a predefined threshold.

At the end of the phase II, descriptive summaries will be provided for all primary and secondary efficacy endpoints. For the primary endpoint, final analysis will take into account the sequential sampling procedure of the design and the underlying binomial distribution assumed by the Simon Two-Stage design.

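### The phase II replacement rule drops early Stable Disease drop-outs that the stated ORR analysis set keeps, so the reported rate can only be raised; the denominator behind ORR0 is not stated

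*Protocol*

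**What the plan says.** All of this is Protocol text on phase II. The SAP states that it covers only the phase I dose escalation, so it does not settle the point.

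- **Section 12.3.1, replacement.** "Nonevaluable subjects will be replaced to meet the above numbers of evaluable subjects". A subject is nonevaluable if there is no evaluation after treatment, or "in case of drop-out before the 4-month visit for PDAC cohort and 8-month visit for CRC cohort with an insufficient follow-up duration", explained as a status still at Stable Disease (SD). The decision rules count evaluable subjects: PDAC stops at 3 or fewer responders in 16 and rejects at 12 or more in 44; CRC stops at 3 or fewer in 19 and rejects at 13 or more in 55.
- **Section 12.3.1, enrolment.** "Assuming a non-evaluability rate of 20% for the PDAC cohort [34] and the CRC cohort [36]", about 55 and 70 subjects are to be enrolled. The 20% is not split between the two kinds of nonevaluable subject.
- **Section 12.3.1, thresholds.** ORR0/ORR1 are 17%/35% (PDAC) and 15%/30% (CRC). For PDAC, "These values reflect the results from PDAC therapy [34] currently registered and are considered standard-of-care"; the CRC ORR0 is an estimated average over cited studies. No denominator is given for either.
- **Section 12.3.2.** "All subjects who receive at least one dose of study drug and who have postbaseline efficacy data for the ORR" enter the primary-endpoint evaluation, with no minimum follow-up.
- **Section 12.3.4.** "The primary endpoint is ORR and will be calculated as defined in RECIST version1.1 and in Section 12.2.7". Section 12.2.7 divides by evaluable subjects, but its definition of evaluable (at least two administrations, end of Cycle 2 or EOCT reached) stands in a paragraph written for phase I. Section 12.3.4 adds that the "final analysis will take into account the sequential sampling procedure of the design".

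**The concern.** A RECIST status of SD requires a scan after baseline. A subject who leaves early at SD therefore has the data that Section 12.3.2 asks for, and is also a subject whom Section 12.3.1 removes and replaces. The other replacement ground, no post-treatment evaluation, does not conflict with 12.3.2.

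The removal depends on outcome. An early drop-out with a response stays in and one at SD goes out; the remaining replaced subjects have no recorded response. The attached RECIST 1.1 text (Attachment 4, RECIST section 4.9.1) says that phase II conclusions should rest on all eligible or all treated patients and not on a selected evaluable subset. The Protocol departs from this without giving a reason.

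At stake are which response rate is reported as primary, and whether that rate is compared with a historical ORR0 counted in the same way.

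**Working it through.** **Inputs.** Section 12.3.1: (n1, r1, n, r) = (16, 3, 44, 11) for PDAC and (19, 3, 55, 12) for CRC, where the cohort stops at r1 or fewer responders and rejects above r; ORR0/ORR1 = 0.17/0.35 and 0.15/0.30; 20% nonevaluable.

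**1. The plan's own figures.** P(reject | p) = sum over x > r1 of Bin(x; n1, p) × P(Bin(n − n1, p) > r − x).

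| Cohort | Alpha at ORR0 | Power at ORR1 |
|---|---|---|
| PDAC | 4.61% | 80.91% |
| CRC | 4.77% | 80.06% |

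An exhaustive search for the optimal design at 5% and 80% returns these same two designs. Enrolment is 44/0.8 = 55 and 55/0.8 = 68.75, so 69, against about 70 stated. The printed design is correct for rates among subjects who are evaluable under 12.3.1.

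**2. Same responders, two denominators.** At 20% nonevaluable, 55 − 44 = 11 PDAC and 69 − 55 = 14 CRC subjects are replaced. The number who are SD drop-outs with a scan is an assumption.

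| Replaced subjects who are SD drop-outs | PDAC | CRC |
|---|---|---|
| 12.3.1 set (all excluded) | 12/44 = 27.3% | 13/55 = 23.6% |
| 12.3.2 set, 6 of 11 and 7 of 14 | 12/50 = 24.0% | 13/62 = 21.0% |
| 12.3.2 set, all 11 and all 14 | 12/55 = 21.8% | 13/69 = 18.8% |

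The numerator never moves, so the count-based decision never moves either.

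**3. Type I error under hypothetical denominators for ORR0.** Suppose ORR0 is an all-treated rate and a fraction q is replaced, all of them non-responders. The null rate among evaluable subjects is then ORR0/(1 − q). At q = 20% this is 0.17/0.8 = 21.25% and 0.15/0.8 = 18.75%.

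| Scenario | Alpha PDAC | Alpha CRC |
|---|---|---|
| q = 10% | 8.8% | 9.3% |
| q = 20% | 16.8% | 17.9% |
| Replaced subjects respond at ORR0 | 4.6% | 4.8% |

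If ORR1 is also an all-treated rate, the rate among evaluable subjects is ORR1/(1 − q). Power is then 90.1%/89.6% at q = 10% and 96.0%/95.7% at q = 20%.

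**The case against.** **The sections can be read together.** Section 12.3.2 could say whose data enter, Sections 12.3.4 and 12.2.7 make the denominator evaluable subjects, and Section 12.3.1 says who is evaluable. The attached RECIST text (section 4.4.3) itself calls a patient inevaluable who is lost after a first SD assessment before the minimum SD duration is met. This stands as a possible reading, so a reader who infers that the Protocol necessarily prescribes two primary rates goes further than the text. But the reading only selects the outcome-dependent subset, and the 4- and 8-month windows are longer than the 6 to 8 weeks that RECIST gives as its general minimum interval for SD.

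**No decision changes.** This is right. The mismatch by itself changes only the reported percentage. Even the lowest rates above, 21.8% and 18.8%, exceed 17% and 15%.

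**Inflation rests on sources not in the documents.** Also right. It needs an ORR0 taken on a wider denominator, which the documents neither state nor exclude.

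**The text is provisional.** Section 4.3 foresees an amendment before phase II, and Section 12.3.1 allows its assumptions to be updated. That makes the repair cheap. It does not remove it: the boundaries and replacement rule are current text, and a new value for ORR0 would still need a stated denominator.

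**Conclusion.** The point holds in a limited form. The replacement rule removes only non-responders or unassessed subjects, Section 12.3.2 keeps some of them, and no section says which set governs. For the same responders, the evaluable rate is equal to or higher than the rate on the 12.3.2 set or on all treated subjects. At the boundary the gap is at most 27.3% against 21.8% (PDAC) and 23.6% against 18.8% (CRC), assuming 20% nonevaluable and every replaced subject an SD drop-out with a scan.

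Three stronger readings are not supported:

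- **That the true type I error is above 5%.** The figures of 8.8% to 17.9% are scenarios. They require an all-treated ORR0 and replaced subjects who are all non-responders.
- **That 5% and 80% hold only if both rates use the 12.3.1 definition.** Power rises above 80% if both rates are all-treated with replaced subjects as non-responders, and alpha is unchanged if replaced subjects respond at ORR0.
- **That CRC evaluability stays open until month 8 for everyone, against a Stage 1 analysis due "no later than after the 16-week visit of the last evaluable subject of the Stage 1 cohort".** The 8-month rule concerns drop-outs at SD only. What is missing is minor: how to treat a CRC subject counted at Stage 1 who later leaves at SD before month 8.

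**What to change.** In the phase II amendment that Section 4.3 already plans:

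1. Make all treated subjects the primary ORR set, with early SD drop-outs and subjects without a post-treatment evaluation counted as non-responders. Keep evaluable-only ORR as a sensitivity analysis. Align Sections 12.3.1, 12.3.2 and 12.3.4, and limit the reference to Section 12.2.7 to the ORR formula.
2. State ORR0 and ORR1 on that same denominator. If both are already all-treated rates, the printed 16/44 and 19/55 designs and boundaries stand. If not, re-derive the design and show its sensitivity to the assumed nonevaluable rate. Converting both rates at 20% gives 21/54 (PDAC; stop at 3 or fewer, reject at 12 or more) and 24/75 (CRC; stop at 3 or fewer, reject at 14 or more), but these should not be adopted as fixed designs. With evaluable rates as printed, their alpha is 9.5%/10.1% if only 10% are nonevaluable, and their power is 72.3%/72.6% if 25% are.
3. If replacement is kept, make Section 12.3.2 match Section 12.3.1 and say that the 5% is against an ORR0 with the same evaluable definition.
4. State how a CRC subject counted at Stage 1 is handled after a later drop-out at SD before month 8.

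**Cost.** Text in an amendment that is due anyway. If both rates are all-treated, 44 + 55 = 99 subjects are treated, against about 125 planned; otherwise the size depends on the re-derivation. The downside is a less favourable reported ORR.
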